Our core technology is the insulin controller, which orchestrates all subcutaneous (SC) insulin dosing. At its centerpiece is a model-predictive control algorithm, which bases insulin doses on the glucose data and insulin absorption kinetics. We were the first to incorporate insulin pharmacokinetics (PK) into the algorithm, by augmenting it with a mathematical formulation for estimating the concentration of insulin in the blood and predicting its future concentration. It is essential to compensate for the slow absorption rate of SC insulin analogs (peak time in blood of 30--90 min, clearance in 4--8 hr), and to enable the algorithm to refrain from stacking and overdosing insulin. Furthermore, the MPC algorithm automatically adjusts its insulin-dosing aggressiveness continuously and in real-time to different insulin needs between individuals and variable needs within the same individual. Running in parallel with the MPC algorithm is an algorithm that automatically modulates basal insulin delivery over multiple time scales, and another algorithm that automatically adapts insulin doses in response to optional meal announcements. Unlike current insulin pumps, and all of the insulin-only control algorithms of which we are aware, the adaptive basal insulin algorithm obviates the need for the user to set, or even know, his or her "basal-rate profile". Instead, it is capable of automatically adapting to, and compensating for, changes in an individual's basal insulin need, such as might occur over a period of hours, days, or weeks (e.g. circadian hormonal fluctuations, intercurrent illness, physical activity, or emotional state) or as might occur over a period of months or years due to developmental changes (e.g. hormonal changes that occur during puberty or menopause). Our adaptive meal dose controller obviates the need for the user to set, or even know, his or her "carbohydrate-to-insulin ratios", as it makes automatic adjustments based on dosing history for similar meal announcements made on previous days, and customizes the dose for each individual and for time of day. Our BP also includes a proportional-derivative algorithm governing SC micro-doses of glucagon to help prevent impending hypoglycemia. Glucagon dosing is based on the glucose level and rate of descent. It could occur preemptively even if glucose is above range and it includes a feedback term to account for the pending effects of recent glucagon doses.

[figure not shown]
[figure not shown]

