- A urine pregnancy test will be performed in female volunteers. If the test is positive the volunteer will be informed of the result and the visit will be ended. The date of the last menstrual period will also be documented, along with usual cycle length, for female subjects.
- Study staff will review any changes in medical history or medications since the last study visit, and obtain an updated medication list. Their current pump settings, including basal rates, carbohydrate ratios and correction factor will be documented.
- A 20 gauge or smaller peripheral I.V. will be placed for monitoring plasma glucose and insulin levels.
- Subjects will be provided with the rapid-acting insulin they usually use.
 - For subjects wearing their own leuc-lock compatible pump, a new reservoir will be filled with insulin lispro, new tubing will be primed and a new infusion set will be placed (either Contact Detach or iLet infusion set). The cannula will be primed as recommended by the manufacturer.
 - For subjects using the study provided pump, their pump settings will be programmed into the study pump. A new reservoir will be filled with insulin lispro and new tubing will be primed. A new infusion set (either Contact Detach or iLet infusion set) will be placed. The cannula will be primed as recommended by the manufacturer.
- A t=0, baseline plasma samples will be drawn for insulin levels, and a baseline blood glucose level will be obtained.
- Subjects will remain fasted for 90 minutes, while their pump (or the study pump) delivers their usual basal rate for this time of day. Non-caloric beverages and black coffee will be allowed.
 - During this time, blood will be drawn from the IV for plasma glucose levels at least every 30 minutes. Blood will be drawn more frequently as needed for hypoglycemia.
 - During this time, Blood will be drawn for plasma insulin levels every 30 minutes.
- A t=90, a 0.1 u/kg dose of insulin will be administered through the pump. Subjects will eat a breakfast of their choice containing carbohydrates appropriate to the insulin dose based on their own carbohydrate ratio and correction factor.
 - After breakfast is completed, subjects will not dose any further insulin and will resume fasting

until the experiment is completed.

- For 2 hours after the insulin injection (t=90 to t=210), blood will be drawn for plasma glucose and plasma insulin levels every 20 minutes.

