- Medical, surgical and social history, allergies and review of systems relevant to inclusion and exclusion criteria
- Medications (prescription and non prescription)
- Type of insulin used in pump
- Average total daily dose in the last 30 days (from pump history)
- Height and weight
- Blood pressure
- Urine HCG (pre-menopausal females)
- Hemoglobin
- Hemoglobin a1c

During Study Visits:

- Insulin analog given
- Basal rates for the duration of the experiment, and carbohydrate ratio and correction factor used for the meal bolus
- Timing and content of the meal eaten, including carbohydrate count
- Timing and amount of insulin dose given for the meal
- Plasma glucose levels at least every 30 minutes, more frequently in the low range
- Plasma insulin levels every 20-30 minutes (assayed with Mercodia Iso-insulin ELISA)
- Total insulin given throughout the experiment
- Timing and amount of any carbohydrates taken for hypoglycemia
- Infusion site assessments including pain, skin reactions, appearance of site, and any evidence of leaks
- Timing of any infusion site replacements
- Subject reports of symptoms of any other complaints
- User satisfaction with both infusion sets

VI. b. Study Endpoints

VI. b. 1. Primary endpoint analyses

Aim 1: This will be generated from the bionic pancreas data during each arm:

- Average percent dose amounts calculated by the bionic pancreas control algorithm that are successfully delivered by the pump (aggregate of both insulin and glucagon doses).

Aim 2:

This will be generated from the bionic pancreas data during each arm:

- Average percent dose amounts calculated by the bionic pancreas control algorithm that are successfully delivered by the pump (glucagon doses).

Aim 4: Insulin Area Under the Curve in the 3.5 hours following the insulin bolus

VI. b. 2. Secondary endpoint analysis – Infusion Set Sub-Study

- During the initial 90 minute fasted period:
 - AUC
 - Mean insulin levels
 - Difference between insulin levels at baseline and at 90 minutes
- After the insulin dose:
 - T_{max}
 - T_{½max}
 - C_{max}
 - AUC in the first 30 minutes
 - AUC in the first 60 minutes
 - AUC in the first 90 minutes
 - Terminal half-life
- Difference between the fasted PG value and the PG value at 90 minutes
- Difference in PG prior to the meal and peak post-prandial glucose
- PG AUC in the 3.5 hours following the meal
- Number of infusion sites replaced for clinically suspected failure
- Local skin reactions
- Infusion site pain

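### Aim 4: the fasted-period insulin AUC and mean largely reflect the previous infusion set, and the measured t=0 insulin level is not used in analysing them

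*Combined protocol and SAP*

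**What the plan says.** The sequence is in Section V.d.5. At the visit "new tubing will be primed and a new infusion set will be placed (either Contact Detach or iLet infusion set"). Then "A t=0, baseline plasma samples will be drawn for insulin levels, and a baseline blood glucose level will be obtained". For the next 90 minutes the plan states: "Subjects will remain fasted for 90 minutes, while their pump (or the study pump) delivers their usual basal rate for this time of day". A bolus of 0.1 u/kg is given at t=90 and sampling ends at t=300. No washout from the previous set is described, and no interval between set placement and t=0 is given.

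Section VI.b.1 makes the primary endpoint "Insulin Area Under the Curve in the 3.5 hours following the insulin bolus". Section VI.b.2 lists, under "During the initial 90 minute fasted period", an AUC, the mean insulin level and "Difference between insulin levels at baseline and at 90 minutes". That last item is the only listed insulin endpoint that explicitly uses the t=0 value.

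The closing paragraphs of Section VI.b plan a paired t-test or a Wilcoxon signed rank test, with no baseline covariate. Section VI.c gives no power calculation for the sub-study. Section VI.d counts it a success if no significant difference in set performance is seen. Section I.b gives the kinetics of subcutaneous insulin as "peak time in blood of 30--90 min, clearance in 4--8 hr".

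**The concern.** Insulin infused before t=0 came through whatever set the subject was wearing on arrival. With clearance over 4–8 hours, much of it is still reaching plasma during the 90-minute fasted window. The fasted AUC and mean therefore mix a large component from the old set with a small one from the set under test.

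Section V.d.5 equalises basal rates, dose and meal during the two experiments, but before them it requires only fasting from midnight. Insulin on board at t=0 can therefore differ between a subject's two visits for reasons unrelated to either set.

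Aim 4 (Section II) asks about set performance in both the fasted and post-prandial states, and success is defined as the absence of a significant difference. A fasted comparison that can hardly register under-delivery would pass almost regardless of how the set performs.

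**Working it through.** Section VI.c states no figure for Aim 4, so there is no planned number to reproduce. The check asks what share of each AUC comes from the previous set, and how the test-set signal compares with the noise that residue brings.

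**Inputs from the protocol:** peak 30–90 min and clearance 4–8 h (I.b); fasted window 0–90 min, bolus 0.1 u/kg at t=90, end at t=300 (V.d.5); up to 10 completers (IV.a).

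**Assumed, not in the protocol:** linear absorption; steady basal delivery before the switch; basal rate 0.005–0.02 U/kg/h; clearance read as 95% cleared; set placed 0–30 min before t=0; a 20% visit-to-visit CV in t=0 insulin.

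**Formulas.** With peak time τ and equal rates, the fraction of the old-set level remaining at time t is S(t) = (1 + t/τ)·exp(−t/τ). Its integral from 0 to T is 2τ − (2τ + T)·exp(−T/τ).
- Fasted share = (integral of S over 0–90) / 90.
- Primary share = b × (integral of S over 90–300) / [b × 210 + 0.1 × (1 − S(210))], with b the basal rate per minute.

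**Central case** (τ = 60 min, 95% cleared at 285 min = 4.75 h, basal 0.01 U/kg/h, set placed at t=0).
- Integral over 0–90 = 120 − 210 × 0.2231 = 73.14. Fasted share = 73.14/90 = 81%.
- Integral over 90–300 = 117.17 − 73.14 = 44.03, and S(210) = 0.136. Primary share = 0.000167 × 44.03 / (0.0350 + 0.0864) = 0.00734/0.1214 = 6.0%.

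**Range**, using two-rate versions that meet both the 30–90 min peak and the 4–8 h clearance:

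| Old-set share | Set placed at t=0 | Set placed 30 min before t=0 |
|---|---|---|
| Fasted AUC | 68–90% (central 81%) | 48–81% (central 65%) |
| Primary AUC | 2–22% (central 6.0%) | 1–18% (central 4.2%) |

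An equal-rate model with a 30-minute peak gives lower fasted shares (58%, or 33% with the gap). It clears in 2.4 h, faster than the protocol's own figure, so it is left out of the range.

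**Signal against noise in the fasted phase**, central case, test set delivering 70% of the comparator:
- Raw AUC: signal = 0.30 × (1 − 0.813) = 5.6% of the AUC. SD of the paired difference from the residue alone = √2 × 0.20 × 0.813 = 23%. The standardised effect is 0.056/0.230 = 0.24. With n = 10 the noncentrality is 0.24 × √10 = 0.77 on 9 df, and two-sided 5% power is about 11%.
- Baseline-to-90-minute change: S(90) = 0.558, so the change, in units of the steady basal level, is 0.442 × (relative delivery − relative t=0 level). Signal = 0.442 × 0.30 = 0.133. SD from the residue = 0.442 × √2 × 0.20 = 0.125. The ratio is 1.06, over four times that of the raw AUC, before assay and other error. Some t=0 variation remains in this measure.
- Simulated 10-subject trials at 70% delivery, with assumed CVs, detected the deficit in about 8–14% of runs with raw fasted AUC, 36–62% with t=0 adjustment, and 37–56% with the change score. The advantage shrinks as assay error grows.

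**Primary AUC.** The same 20% CV adds √2 × 0.20 × 0.060 = 1.7% to the SD of the paired difference. A set delivering 80% would show a ratio of 1 − 0.20 × 0.94 = 0.81. In simulation, a t=0 covariate made the primary confidence interval about 2–8% wider.

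**Cost of a covariate at n = 10.** CI width ratio = √[(1 − r²) × 9/8] × 2.306/2.262. This gives 1.08 at r = 0, 0.94 at r = 0.5 and 0.77 at r = 0.7, with break-even near r = 0.38.

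**The case against.** The strongest reply is that the planned tests work on within-subject differences. A residue equal at both visits drops out exactly, leaving the difference, its SD and the p-value unchanged. Visit order is randomised, so any imbalance favours neither set systematically. The bolus window is dominated by test-set insulin. The baseline-to-90-minute change is already listed. Failure is also sought through Cmax, Tmax, glucose endpoints, site replacements and hourly site checks. The protocol calls the sub-study a pilot, and every magnitude above rests on an assumed model.

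Most of this stands, and it disposes of two stronger readings that a reader might infer. The first is that old-set insulin materially distorts the primary AUC. The central share is about 6% and the added noise about 1.7%, so it does not. The second is that a shared residue by itself pulls the planned test toward no difference. That would hold for a ratio judged against a margin, but the documents plan a paired difference and set no margin. Nor do they prescribe uncorrected AUCs in so many words; they simply specify no correction.

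Cancellation covers only the shared part of the residue. Visit-to-visit variation stays in the paired difference, and in the fasted window it is carried by a component about four times as large as the test set's own (81% against 19%). Randomised order prevents bias but does not remove that noise with 10 subjects. Listing the change score alongside AUC and mean, unranked, does not tell a reader which to believe if they disagree.

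**Conclusion.** The point holds for the fasted-period AUC and mean insulin, and only there. On the protocol's kinetics most of that AUC is previous-set insulin: about 68–90% with the set placed at t=0, and about 48–81% with a 30-minute gap, so "most" can fail at the fast end. A raw comparison has little ability to show under-delivery, with roughly 11% power in the central case for a set delivering 70%. A non-significant result there should not be counted as evidence that the set performs well.

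The primary AUC needs no change. Its old-set share is about 6% (2–22% across the assumed kinetics and basal rates), and a t=0-adjusted version could be at most a sensitivity analysis.

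All magnitudes are illustrative. They depend on the absorption model, the basal rate, steady delivery before the switch, the unstated placement-to-t=0 interval and an assumed CV for t=0 insulin. The direction for the fasted phase follows from the protocol's own peak and clearance times.

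**What to change.** In Section VI.b.2, for the fasted phase:

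- Name the already listed baseline-to-90-minute insulin change as the lead endpoint.
- Analyse fasted AUC and mean as the within-subject difference in log value between sets, with the within-subject difference in log t=0 insulin as covariate. Use t=0 and not t=90, because the test set has already acted by t=90.
- Do not subtract a constant t=0 level from the AUCs. The residue decays and the new set's own basal insulin would be removed with it. In the central case this takes out 210/44.03 = 4.8 times the true old-set area from the primary AUC, and 90/73.14 = 1.2 times from the fasted AUC.
- State that the covariate reduces noise but does not undo dilution. A set delivering 70% would still show a fasted AUC ratio of about 1 − 0.056 = 0.94, so that ratio must not be read as relative delivery.

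Leave the primary analysis as planned. Recording the time of set placement would help interpretation.

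The cost is SAP wording, since the samples are already scheduled. The covariate uses one degree of freedom, so the interval is up to about 8% wider if t=0 insulin is unrelated to the endpoint. The change score rests on two single samples per visit and is exposed to assay error in each.

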Volunteers who fit the selection criteria will be considered as candidates for this study. We will contact individuals who have previously inquired about participation in our studies and have asked us to have their contact information kept on file. In addition, advertisements for the study may be posted at the MGH Diabetes Center and other places, and may be distributed in the weekly broadcast email of research studies seeking volunteers. A letter may be sent to adult endocrinologists in the Boston metropolitan as well as selected nearby endocrinologists informing them of the study and asking them to refer any eligible patients who might be interested. We will post information about the trial along with contact information on our website

www.bionicpancreas.org and on www.clinicaltrials.gov.

IV. Subject Enrollment

IV. a. Number of Subjects

It is expected that we will have up to 10 subjects complete the study with a consistent protocol. We expect that the experiments can be accomplished over a period of 6 months. Up to 20 subjects with type 1 diabetes will be enrolled. The upper bound is based on the expectation that some volunteers will be excluded after the screening visit and the possibility that some experiments may have to be discontinued before completion (due to, for instance, intercurrent illness or subject withdrawal).

It is expected that we will have up to 10 subjects complete the Infusion Set Sub-Study with a consistent protocol. We expect that the experiments can be accomplished over a period of 6 months. Up to 20 subjects with type 1 diabetes will be enrolled. The upper bound is based on the expectation that some volunteers will be excluded after the screening visit and the possibility that some experiments may have to be discontinued before completion (due to, for instance, intercurrent illness or subject withdrawal).

The total enrollment for the study, including the infusion set sub study will be up to 40 subjects.

IV. b. Enrollment Procedures

Prospective participants will be briefed by a study staff member by phone or secured e-mail (using the "Send Secure" encryption) regarding the study procedure and the inclusion and exclusion criteria. Potential subjects will be sent an informed consent document by mail, fax, or secured e-mail. Subjects will be discouraged from discussing medical issues by non-secure e-mail, according to institutional policy.

IV. c. Consent Procedures

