 - Fraction of time spent within each of the following glucose ranges:
 - < 50 mg/dl.
 - < 60 mg/dl.
 - < 70 mg/dl.
 - 70-120 mg/dl.
 - 70-180 mg/dl.
 - >180 mg/dl.
 - >250 mg/dl.
 - Percentage of subjects with mean CGM glucose < 154 mg/dl (estimated average glucose corresponding to an A1c of 7%).
- Number of severe hypoglycemic events (subject unable to self-treat, requiring the assistance of another person).

During Exercise

- Number of subjects discordant for reaching a BG < 60 mg/dl (measured with YSI) for > 2 consecutive plasma glucose measurements
- Area between the glucose curve and 60 mg/dl calculated from BG measurements
- Area between the glucose curve and 60 mg/dl calculated from CGM data
- Time from start of exercise to first BG measurement < 60 mg/dl
- Time from start of exercise to first CGM measurement < 60 mg/dl

VI. b. 5. Secondary endpoint analyses – Non-glycemic

- Glucagon total delivery per kg of body mass.
- Insulin total delivery per kg of body mass.
- Number of episodes of symptomatic hypoglycemia.
- Number of carbohydrate interventions for hypoglycemia.
- Total grams of carbohydrate taken for hypoglycemia.

- Difference in mean nausea from VAS during the study (mean of measurements every 2 hour and at study end) vs. baseline at study start.
- Difference in Infusion site pain from VAS during the study (mean of measurements every 2 hour and at study end) vs. baseline at study start. Note that in the iLet infusion set the infusion catheters are 1 cm apart, so it may not be possible to differentiate whether a sensation is coming from the insulin or glucagon infusion catheter. Subjects will be asked to use their best judgment and to provide scores for both catheters.
- Difference in local erythema and edema according to the Draize scale (mean of measurements every 2 hour and at study end) vs. baseline at study start. Note that in the iLet infusion set the infusion catheters are 1 cm apart, so it may not be possible to differentiate whether a skin reaction is coming from the insulin or glucagon infusion catheter. Subjects will be asked to use their best judgment and to provide scores for both catheters.
- Number of unscheduled infusion set replacements.
- Number of unscheduled CGM sensor changes.

During Exercise

- Grams of oral carbohydrates given to the subject to treat hypoglycemia
- Total glucagon dosing by bi-hormonal bionic pancreas from the start of exercise until the end of the visit

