The primary analysis of the designated endpoints will be calculated on an intention-to-treat basis. In cases where an arm was not completed (and that arm was not repeated according to protocol criteria) we will use the available data from that arm in the data analysis. We will only include arms that were started by the subject.

We will use the Shapiro-Wilk test to determine the normality of the residuals for each comparison and calculate percentages, means or medians, and standard deviation and/or ranges as appropriate in descriptive analyses. We will use paired t-test or the Wilcoxon signed rank test for comparison of means with normally or non-normally distributed residuals, respectively. In a secondary analysis we will look for any period effect and any interaction between treatment and period, although no such interaction is predicted for the primary outcome, and there is probably insufficient power to identify a small interaction.

VI. c. Power Analysis

The power analysis is based on data from previous studies using the iPhone-based BP. The following table shows the percentage of time that the insulin and glucagon pumps were available to deliver doses calculated by the bionic pancreas. When pumps were not available, this was typically due to loss of communication between the iPhone and the t:slim pumps, but could also be due to pump occlusion or inadequate drug in the reservoir, among many other possible reasons.

Table 1. Time that pumps were available in previous bionic pancreas studies

| Study | insulin | | Glucagon | |
|------------------------------|---------|-----|----------|-----|
| | Mean | SD | Mean | SD |
| Beacon Hill | 96.5 | 2.7 | 95.9 | 2.3 |
| Camp1 | 93 | 2.7 | 92.2 | 2.3 |
| Camp2 | 95.1 | 2.5 | 93.9 | 3.1 |
| Multi-center | 96.1 | 2.5 | 95.9 | 2.5 |
| Mean | 95.2 | 2.6 | 94.5 | 2.6 |
| Min | 93.0 | 2.5 | 92.2 | 2.3 |
| Max | 96.5 | 2.7 | 95.9 | 3.1 |
| ttest (insulin vs. glucagon) | | | 0.044 | |

The glucagon pump was unavailable a greater percentage of the time than the insulin pump in the iPhone-based BP. This could be due to more frequent reservoir changes (the glucagon reservoir had to be changed every day, while the insulin reservoir was changed every other day – the pumps were unavailable during the reservoir change process), greater number of occlusions in the glucagon tubing and infusion sets, or possibly other, unknown factors.

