We anticipate that the iLet BP will be much more reliable in terms of delivering calculated doses because it does not rely on wireless communication between the device running the control algorithm and the pumps. In the iLet, the control algorithm and pumps are integrated into a single device. Nonetheless, there may still be times that the pump is unavailable or that the full dose is not delivered (e.g. due to temporary loss of communication between components due to software issue, tubing occlusion, or inadequate drug in the reservoir). Therefore, we anticipate that the percentage of the dose amount calculated that are delivered will be substantially greater, but not 100%.

We have modeled the power to detect a difference between the iPhone-based and iLet BPs based on an aggregate rate of pump unavailability of the iPhone-based BP (including both the insulin and glucagon pumps) of $96\pm 2.5\%$, which is close to the maximum reliability that we observed in the more reliable insulin pump across the 4 previous studies. We then calculated the power based on different possible reliabilities of the iLet internal pumping systems, based on 2-fold, 5-fold, and 10-fold reductions in pump unavailability, corresponding to availabilities of $98\pm 2.5\%$, $99.2\pm 2.5\%$, and $99.6\pm 2.5\%$, respectively. Under these assumptions, the sample sizes required for each of these possible outcomes to achieve a power of 80% with an alpha of 5% using a 2-sided test are 25 subjects, 10 subjects, and 8 subjects respectively. We expect a reduction of at least 5-fold in pump unavailability (and 10-fold would not be surprising), so 10 subjects should provide sufficient power to detect a difference. The standard deviations are assumed to be unchanged in these calculations, although it is likely that the standard deviations would also be reduced if the pump becomes more reliable - this means that the sample size estimates are likely conservative.

As the Infusion Set Sub-Study is a pilot study of the modified infusion set, no formal power calculations have been done for this portion of the study.

VI. d. Criteria for Success of the Study

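### The two exercise endpoints that time the first glucose below 60 mg/dl have no value when that level is never reached, and the named paired tests come with no rule for such visits.

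*Combined protocol and SAP*

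**What the plan says.** Under the During Exercise subheading of Section VI.b.4 the plan lists two timing endpoints: "Time from start of exercise to first BG measurement < 60 mg/dl" and "Time from start of exercise to first CGM measurement < 60 mg/dl". It gives no censoring rule, substitute value or end of observation for either.

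The closing paragraphs of Section VI.b name the between-arm tests: "We will use paired t-test or the Wilcoxon signed rank test for comparison of means with normally or non-normally distributed residuals, respectively". The only rule for incomplete data there is "we will use the available data from that arm in the data analysis", and it applies to arms that were not completed. A completed visit in which glucose never falls below 60 is not such an arm.

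On numbers, Section IV.a states: "It is expected that we will have up to 10 subjects complete the study with a consistent protocol".

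The same During Exercise list also has a count of subjects discordant for a YSI glucose below 60 on more than 2 consecutive measurements, and the area between the glucose curve and 60 mg/dl from both BG and CGM.

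**The concern.** A time to first value below 60 exists only if the event happens. A paired t-test or signed-rank test can use a subject only when both visits being compared supply a time. If nothing else is specified, the analysis shrinks to subjects who went low on both systems. A subject who went low on one system and not on the other leaves the comparison, although that contrast is what an exercise-hypoglycemia endpoint should capture. Membership of the analysed set then depends on the outcome, and with so small a trial few pairs may be left.

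The end of observation is also open. Exercise lasts about 30 minutes and starts at Hour 5-6 of a visit of at least 8 hours (Section V.d.4), which leaves roughly 2 to 3 hours to the end of the visit. One exercise endpoint in Section VI.b.5 runs expressly to the end of the visit; the two timing endpoints do not say whether they do.

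**Working it through.** **The plan's own figures.** Section VI.c gives 25, 10 and 8 subjects "to achieve a power of 80% with an alpha of 5% using a 2-sided test". With SD 2.5 and differences of 2.0, 3.2 and 3.6 points, n = 2 × (1.96 + 0.84)² × 2.5² / difference² gives 24.5, 9.6 and 7.6, which round up to 25, 10 and 8. The figures reproduce, but they concern pump reliability, the primary endpoint. No event rate, sample size or power is given for the timing endpoints.

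**Inputs for the check.**
- Subjects: at most 10 (Section IV.a).
- p, the chance that a visit reaches <60 after exercise starts: not in the documents; assumed 30%, 50% and 70%.
- r, the within-subject correlation of reaching <60: not in the documents; from 0 (independent visits) to 1 (complete overlap).

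Section I.c reports 0.6 to 1.5% of CGM time below 60 on the bionic pancreas. That is a share of time in multi-day use, not a per-visit probability after exercise, so it is not used to set p.

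**Complete pairs.** P(both visits reach <60) = p² + r·p(1−p). Expected pairs are 10 times this.

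| p | r = 0 | r = 1 | Chance of at least 6 pairs (r = 0 to 1) |
|---|---|---|---|
| 30% | 10 × 0.09 = 0.9 | 10 × 0.30 = 3.0 | 0.000 to 0.047 |
| 50% | 10 × 0.25 = 2.5 | 10 × 0.50 = 5.0 | 0.02 to 0.38 |
| 70% | 10 × 0.49 = 4.9 | 10 × 0.70 = 7.0 | 0.35 to 0.85 |

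The last column is the binomial upper tail with 10 subjects. An 80% chance of at least 6 pairs needs p of about 82% if visits are independent, or about 67% with complete overlap.

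**What the tests can do with few pairs.** The smallest two-sided signed-rank p-value with m untied pairs is 2/2^m: 0.0625 for m = 5 and 0.031 for m = 6. A paired t-test has no such floor, but little power. As an illustration, take the standardised difference implied by the plan's middle scenario with uncorrelated visits, 3.2/(2.5 × √2) = 0.905. Power at two-sided 5% is then 16% with 3 pairs, 34% with 5 and 72% with 10.

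**If 'not reached' is ranked as the longest time.** A pair is informative when at least one visit reaches <60. Under independence the expected number is 10 × [1 − (1−p)²]: 5.1 at 30% and 7.5 at 50%, against 0.9 and 2.5 complete pairs. Under complete overlap there are no discordant subjects to recover, and the number stays at 10p: 3 and 5.

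**The case against.** The strongest reply is that the plan is silent rather than wrong. It does not tell the analyst to drop anyone, and it does not tie the two tests to these endpoints by name. The secondary lists also hold counts and a list of technical faults, which no paired t-test could take, so the test sentence is not a literal rule for every item, and the plan allows for descriptive summaries. This stands: a reader might infer that exclusion is prescribed, but it is only what the named tests do when no rule is given.

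Second, neighbouring endpoints keep subjects who never reach 60. The area measures are zero for them, and the discordance count compares arms directly. This stands in part. The area measures capture depth and duration rather than timing. The discordance count requires more than 2 consecutive YSI values, so a brief dip does not count, and it has no CGM counterpart.

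Third, the event rate is unknown. The algorithm starts from body weight alone and the visit includes an exercise challenge, so events need not be rare. At 70% per visit, 6 or more pairs could well remain. This also stands.

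Fourth, a reader might infer that the analysis is biased toward no difference, and so favours the Section VI.d criterion of no significant difference in glycemic control. The documents do not support that. If one system prevented mainly late events, those left in its arm would be the earlier ones, and complete pairs could make it look worse. Nor does Section VI.d say which glycemic measures count; Section II singles out mean CGM glucose and percent time below 60 as the important ones.

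**Conclusion.** The gap is real and small. Two secondary endpoints are undefined for an outcome that can occur at any visit, and the only tests named cannot use such visits. A complete-pair analysis would be selected on the outcome and blind to prevention in one arm, with a bias of unknown direction. Too few pairs for a signed-rank test is likely at event rates up to about 50% and not certain above that; this rests on assumed rates and on no more than 10 subjects. The trial's assessment of exercise hypoglycemia as a whole is not lost, because the companion endpoints cover part of it.

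**What to change.** Add a short rule to Section VI.b:

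- Set one observation window common to the visits being compared, for example from the start of exercise to a fixed time no later than the end of the visit.
- Treat a visit that does not reach <60 as censored at the window end and rank it as the longest time.
- Compare arms within subject with a sign test or a paired Prentice-Wilcoxon test, naming one in advance.
- Report beside it the number of subjects reaching <60 in each arm.
- Apply the same rule to the CGM version.

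This needs no new data. The costs are that subjects who reach 60 at neither visit are tied and uninformative, that a sign test gives up some timing information, and that power stays low: at 30% per visit even the recovered set averages 5.1 pairs or fewer. The result should therefore be labelled descriptive. Settling the rule before the data are seen avoids a choice made after the event pattern is known.
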